## 4 STUDY DESIGN

### 4.1 OVERALL DESIGN

- *A statement of the hypothesis.*
  - To test the hypothesis that ScNS can be used to reduce the AF burden in patients with paroxysmal AF
- *Phase of the trial.*
  - Not applicable.
- *A description of the type/design of trial to be conducted (e.g., randomized, placebo-controlled, double-blinded, parallel design, open-label, dose escalation, dose-ranging, adaptive, cluster randomized, group sequential, multi-regional, superiority or non-inferiority design).*
  - This is a prospective randomized IDE study. The patients are randomized into Experimental and Control groups. There is an option for the Control group to crossover into the Experimental group after completion of obtaining the primary endpoint.
- *A description of methods to be used to minimize bias.*
  - The investigators are responsible for programming the device and cannot be blinded to the study. However, we will not tell the patients whether they are randomized into the experimental or the control group until the primary endpoint is complete. Technicians and physicians responsible for echocardiogram and ECG monitoring will be blinded.
- *The number of study groups/arms and study intervention duration.*
  - We will randomize the patients into:
    - Group A: Experimental group will undergo 3.5 mA ScNA for two weeks.
    - Group B: Sham control group will receive 0 mA stimulation for two weeks.

- *Indicate if single site or multi-site.*
  - This is a single site study.
- *Name of study intervention(s).*
  - Subcutaneous nerve stimulation (ScNS).

## 4.2 SCIENTIFIC RATIONALE FOR STUDY DESIGN

Medical device is known to have strong placebo effects. Therefore, we chose to perform a prospective randomized study with a sham control group. The only difference between experimental and sham control groups is the strength of neurostimulator output (3.5 mA versus 0 mA).

## 4.3 JUSTIFICATION FOR DEVICE SETTING

Our recent studies in canine models showed that ScNS may be either proarrhythmic or antiarrhythmic depending on the stimulus strength. Very low strength (0.5 mA) ScNS causes nerve sprouting and increases plasma norepinephrine concentration, leading to increased cardiac arrhythmia in ambulatory dogs. On the other hand, high output (3.5 mA) ScNS is antiarrhythmic. Because of these findings, we will only use 3.5 mA output in the Experimental group. No patients will receive low output stimulation.

## 4.4 END OF STUDY DEFINITION

A participant is considered to have completed the study if he or she has completed all phases of the study including the last visit shown in the Schedule of Activities (SoA), Section 1.3.

# 5 STUDY POPULATION

## 5.1 INCLUSION CRITERIA

In order to be eligible to participate in this study, an individual must meet all of the following criteria:

- 18 to 75 years of age
- Symptomatic paroxysmal AF unresponsive to conventional therapy.
  - Symptomatic paroxysmal AF is defined by paroxysmal AF with patient-reported perception of one or more of the following symptoms: palpitations, dizziness/presyncope, syncope, dyspnea, chest pain, malaise, and fatigue and activity intolerance.
  - There is at least one ECG-documented AF episode.
  - Unresponsive to conventional therapy is defined by not responding to at least 1 antiarrhythmic drug (class I, class III, or atrioventricular nodal blocker).

- The left atrial size <50 mm by transthoracic echocardiography documented by eligibility visit
- Documented atrial fibrillation as defined as atrial fibrillation >30 seconds in duration with an atrial fibrillation burden determined by a minimum of 7 days of continuous ePatch monitoring within 6 months before surgery.

## 5.2 EXCLUSION CRITERIA

An individual who meets any of the following criteria will be excluded from participation in this study:

- Patients without AF episodes during monitoring period will be excluded from the study and count as screen failure
- Left ventricular ejection fraction <40%
- Heart failure with functional classes III or IV
- Recurrent vasovagal syncope
- Valvular AF (severe mitral regurgitation, mitral stenosis)
- Congenital heart diseases
- Wolff Parkinson-White Syndrome
- Stroke within the past 6 months
- Any history of myocardial infarction
- Malignancies with a life expectancy of < 1 year
- A history of ablation procedures to treat left atrial tachyarrhythmias or other serious comorbidity
- Any history of sustained ventricular tachycardia (VT) defined by (1) > 30 s in duration or (2) < 30 s in duration, but is associated with hemodynamic consequences such as hypotension and syncope.
- Patients with a vagal nerve stimulator
- Active thyrotoxicosis
- Sick sinus syndrome with symptomatic bradycardia
- Heart rate < 50 beats per minute in sinus rhythm on 12-lead ECG
- Systolic blood pressure < 90 mm Hg
- Any experimental medication concomitantly or within 4 weeks of participation in the study
- Subjects with cardiac implantable electronic device (CIED) such as pacemakers and implantable cardioverter-defibrillators (ICDs)
- Pre-existing neuromodulation devices, such as vagal nerve stimulators, spinal cord stimulators and sacral nerve stimulators
- People with a history of allergy to ECG electrodes, adhesive tape, or nylon
- Pregnant women

## 5.3 LIFESTYLE CONSIDERATIONS

During this study, participants are asked to:

- **Day before the implant:**
  - Plan to use the wash 2 times. Once the night before procedure, and again the morning of your procedure.
  - Use about 2 oz. or ¼ cup with each wash

- Take a complete bath or shower with regular soap. Then get a clean wash cloth.
- Do not use Hibiclens soap on your face, ears, or hair
- Use Hibiclens soap on the neck, chest, as far as they can reach over the shoulder and down to the waist, your arms down to the elbows and under the arms
- A gentle wash is good, rubbing and scrubbing is not necessary. Leave on the skin for 1 minute, then rinse off
- Use clean fresh towels and washcloths each time
- The night before the procedure, dress in fresh clean pajamas and sleep on fresh clean sheets
- Dress in fresh, clean clothes after the morning bath/shower to come to the hospital
- Please do not put on lotion, cream, powder, or deodorant after the bath or shower
- Nothing to eat or drink starting at midnight the night before surgery
- Required driver for all patients the day of surgery

- **After implant:**

- Sponge bath only until the device is removed
- Do not get the dressing wet. Remember electricity and water do not mix
- No ointments, powders, lotions, creams, or antibiotic medications on the implant site
- Abstain from driving during the time the lead is implanted
- No bending, lifting, or twisting
- No elbows above your ears, and no reaching up, over, across, or down
- Your lifting limit is 5 lbs, which is approximately a half gallon of milk
- No strenuous activities like yard work, vacuuming, lifting laundry baskets or grocery sacks
- If you smoke, stop. Smoking is not health and can make pain worse, and prolongs healing time
- No driving or operating machinery, making legal decisions, work, or drinking alcohol until the study is completed
- May use ice packs on the implant site dressing, but no heat. Heat will affect the way the stimulator works

## 5.4 SCREEN FAILURES

Screen failures are defined as participants who consent to participate in the clinical trial but are not subsequently randomly assigned to the study intervention or entered in the study. Patients without AF episodes during monitoring period and have an ejection fraction (EF) less than 40% will be excluded from the study and count as screen failure. A minimal set of screen failure information is required to ensure transparent reporting of screen failure participants, to meet the Consolidated Standards of Reporting Trials (CONSORT) publishing requirements and to respond to queries from regulatory authorities. Minimal information includes demography, screen failure details, eligibility criteria, and any serious adverse event (SAE).

## 5.5 STRATEGIES FOR RECRUITMENT AND RETENTION

- Sample size: Total of 30 subjects-15 males and 15 females between 18 and 75 years old.
- Anticipated accrual rate: 30 subjects over 36 months
- All subjects will be enrolled at one US site
- Vulnerable subjects will not be recruited
- All sex, racial and ethnic group members will be recruited to participate in the study

Investigators and co-investigators will approach eligible subjects about the study in person at clinical visits. The patients will be consented by investigator or one of the co-investigators utilizing the informed consent form as a guide. After the questions about the research have been answered the patient will be asked to sign the form. We plan to distribute the study brochure to physicians' offices to help patient recruitment. We will include the study information in the Smidt Heart Institute Current Research website. We do not plan to use any other advertising material.

Subjects will receive payment in the form of a reloadable card for study visits completed. They will not receive more than \$600.00 total or \$900.00 total for study participation depending if they are randomized in the experimental group or control group, respectively. In addition to stipend, the patient will also receive parking passes.

## 6 STUDY INTERVENTION

### 6.1 STUDY INTERVENTION(S) ADMINISTRATION

#### 6.1.1 STUDY INTERVENTION DESCRIPTION

##### Device Information:

- Medtronic spinal cord stimulation 60-cm trial Lead, model No. 977D260.
- Medtronic wireless external neurostimulator (WENS, model 97725).
- Medtronic Neuromodulation Clinician Programmer (App A710)
  - Description of each component
    - Medtronic spinal cord 60 cm trial lead and wireless external neurostimulator are designed to deliver electrical stimulation for the subcutaneous nerve stimulation (ScNS)
    - Medtronic Neuromodulation Clinician programmer will allow the programming of the lead to be set at 3.5mA to deliver the protocol required electrical stimulation
  - Device settings and programming- The programming of the lead will set at 3.5mA in the experimental group
  - Duration of implant Subjects will have the Medtronic neurostimulator lead implanted subcutaneously for 2 weeks
  - Device has not been approved or cleared for the indications the protocol is designed to investigate. Investigator has obtained an IDE for this protocol. See FDA IDE approval letter

The following device will be donated by Medtronic Inc. for implantation: Medtronic spinal cord stimulation 60-cm trial Lead, model No. 977D260 and Medtronic wireless external neurostimulator

(WENS, model 97725). These devices are currently FDA approved for pain control through spinal cord stimulation.

This IDE study is funded by NIH. Medtronic Inc. will donate the device. The final labeling of the device may change according to the results of the study.

#### 6.1.2 DEVICE ENERGY AND ADMINISTRATION

The experimental group will receive stimulation ScNS at 3.5mA output, while the control group will receive no stimulation for 2 weeks.

The control group will have an option to crossover to the experimental group after three weeks from the first procedure and receive stimulation ScNS at 3.5 mA output.

### 6.2 PREPARATION/HANDLING/STORAGE/ACCOUNTABILITY

#### 6.2.1 ACQUISITION AND ACCOUNTABILITY

Medtronic Inc will donate the following devices for this trial:

Medtronic spinal cord stimulation 60-cm trial Lead, model No. 977D260.

Medtronic wireless external neurostimulator (WENS, model 97725).

These devices are approved by FDA for human use, but an investigator-initiated IDE will be required. This allows the trial to be conducted using the devices for symptomatic atrial fibrillation unresponsive to conventional therapies.

Indications for Use: Symptomatic atrial fibrillation unresponsive to conventional drug therapies.

The unused devices will be returned to Medtronic, Inc.

Accountability of the device will be tracked by the study team using a device accountability log. The log will track the inventory of the device including device type, serial number, and expiration date. All devices used on subjects will be also tracked in Red Cap.

#### 6.2.2 FORMULATION, APPEARANCE, PACKAGING, AND LABELING

Medtronic Inc has committed to donate FDA approved neurostimulator units and nerve stimulation lead for the study. These devices are designed to deliver electrical stimulation of internal organs such as spinal cord and bladder. All devices are FDA approved for human implantation with specific clinical indications. However, because ScNS is not an approved indication, we have obtained Investigator-initiated IDE approval. All devices will be recorded in the redcap database. After the study, the unused devices will be returned to the manufacturer.

#### 6.2.3 PRODUCT STORAGE AND STABILITY

Devices will be sent to CSMC – Smidt Heart Institute and received by clinical research coordinator. These will be stored on a safety cabinet located at the Cath lab after accountability log completed.

#### 6.2.4 PREPARATION

The device comes in a sterile package. It is opened in a sterile manner at the time of procedure. The Medtronic 60cm lead is connected to the Medtronic wireless external neurostimulator (WENS, model 97725). The device is programmed by using the Medtronic Neuromodulation Clinician programmer App A710.

### 6.3 MEASURES TO MINIMIZE BIAS: RANDOMIZATION AND BLINDING

The patient will be consented to undergo surgery. After the device implantation, the patients will be randomized to experimental and control groups using Redcap. We will attempt to blind the patients, although the tingling or pain associated with the stimulation may make blinding difficult. All data analyses performed by the co-investigators and the rhythm analyses performed by the Mobile Cardiac Telemetry system technicians will be blinded. The experimental group will receive stimulation at 3.5 mA output, while the control group will receive no stimulation. Data will be obtained during this time to determine atrial arrhythmia frequencies in both groups. The device will then be removed at the end of the second week. After the third week, we will give the option to the control group to crossover to the experimental group. This group of patients will undergo a second procedure to receive stimulation at 3.5 mA and we will follow up for another 3 weeks and 3 months post second procedure.

We will tell the patients that they will be randomized into experimental group or control group during surgery. We will attempt to blind the patients, although the tingling or pain associated with the stimulation may make blinding difficult. We will explain to all patients they may or may not feel tingling and/or pain during the 2-week stimulation time but will not tell them which group they are assigned to. All data analyses performed by the co-investigators and the rhythm analyses performed by the 7-day non-invasive monitoring system technicians will be blinded. After 3 weeks post-procedure, we will unblind the control group to give them the option of crossing over to the experimental group to receive the treatment. If they agree, these group of patients will forego the 3-month follow-up visit and will proceed with a second procedure along with follow up visits post-second procedure. Data will be obtained during this time to determine AF burden in all groups.

### 6.4 STUDY INTERVENTION COMPLIANCE

The study team will assess compliance with the study intervention by:

- Maintaining accurate study records and documentation of all required visit tests and procedures
- All research staff will be trained in all study activities
- All research staff will be trained in using the HIPAA compliant Redcap electronic data capture system
- Continuous inpatient telemetry. The patient will be continuously monitored in the hospital based on the Principal Investigator's discretion. Additional ECG electrodes will be used for telemetry recordings. The ECG signals will be transmitted to the heart station staffed by experienced technicians for heart rhythm monitoring.

- Outpatient rhythm monitoring. The patient will undergo continuous outpatient near real time telemetry using a Mobile Cardiac Telemetry system. Significant arrhythmia episodes will be reported to the PI or one of the co-investigators for management.
- An Apple watch will be used to monitor AF between Baseline visit and at the end of the study.
- All tests, labs and procedures will be reviewed by a designated research team member
  - Any abnormal result will be reported to the PI immediately

## 6.5 CONCOMITANT THERAPY

- Current medications will be recorded at the baseline visit
- Documentation that patient has been treated with at least 1 antiarrhythmic drug (class I, class III, or atrioventricular nodal blocker)
- In patients treated with warfarin, the investigators will review the data to determine if the INR was > 2.0 for at least a month prior to procedure. In addition, the surgery will not be performed if the INR is > 3.0. For patients on DOAC, we will interview the patient to ensure compliance.

We plan to perform the implant procedures with uninterrupted anticoagulation to reduce the possibility of stroke. We estimate that the small bleeding risk does not justify interruption of anticoagulation in most patients.

### 6.5.1 RESCUE MEDICINE

Not applicable.

## 7 STUDY INTERVENTION DISCONTINUATION AND PARTICIPANT DISCONTINUATION/WITHDRAWAL

### 7.1 DISCONTINUATION OF STUDY INTERVENTION

The study intervention is the subcutaneous nerve stimulation with an externalized neurostimulation lead. The electrical stimulation may be terminated when there are serious adverse events or when patient declines to continue with the stimulation. Discontinuation from electrical stimulation does not mean discontinuation from the study, and remaining study procedures should be completed as indicated by the study protocol. If a clinically significant finding is identified (including, but not limited to changes from baseline) after enrollment, the investigator or qualified designee will determine if any change in participant management is needed. Any new clinically relevant finding will be reported as an adverse event (AE).

The data to be collected at the time of study intervention discontinuation will include the following:

- The reasons for discontinuing the subcutaneous nerve stimulation
- The removal of the subcutaneous electrodes
- Any adverse events

## 7.2 PARTICIPANT DISCONTINUATION/WITHDRAWAL FROM THE STUDY

Participants are free to withdraw from participation in the study at any time upon request.

An investigator may discontinue or withdraw a participant from the study for the following reasons:

- Pregnancy
- Significant study intervention non-compliance
- If any clinical adverse event (AE), laboratory abnormality, or other medical condition or situation occurs such that continued participation in the study would not be in the best interest of the participant
- Disease progression which requires discontinuation of the study intervention
- If the participant meets an exclusion criterion (either newly developed or not previously recognized) that precludes further study participation
- Participant unable to receive subcutaneous nerve stimulation after the electrode is implanted for any reason.

The reason for participant discontinuation or withdrawal from the study will be recorded on the Case Report Form (CRF) using the Redcap database. Subjects who sign the informed consent form and are randomized but do not receive the study intervention may be replaced. Subjects who sign the informed consent form, and are randomized and receive the study intervention, and subsequently withdraw, or are withdrawn or discontinued from the study, will not be replaced.

Based on the results of the canine study, reduced sympathetic nerve discharges may be associated with reduced heart rate. Therefore, we will terminate the study if the patients are found to have the following symptoms/signs which require cardiac pacemaker implantation according to the current ACC/AHA guidelines:

1. Third-degree AV block at any anatomic level associated with any one of the following conditions:
  - a. Bradycardia with symptoms presumed to be due to AV block.
  - b. Arrhythmias and other medical conditions that require drugs that result in symptomatic bradycardia.
  - c. Documented periods of asystole  $\geq 3.0$  seconds or any escape rate  $<40$  beats per minute (bpm) in awake, symptom-free patients.
2. Second-degree AV block regardless of type or site of block, with associated symptomatic bradycardia.

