## 2.3 RISK/BENEFIT ASSESSMENT

### 2.3.1 KNOWN POTENTIAL RISKS

The Immediate risks include the risks associated with surgery such as pain, allergic reaction to the drugs used during surgery, bleeding and death. The possibility of a second surgery increases the previous risks.

The long-range risks include the following:

Because ScNS remodels the stellate ganglion and reduces sympathetic outflow, it is possible to slow down the sinus rate or atrioventricular (AV) conduction. If the following serious side effects are observed, the ScNS will be terminated:

- Third-degree AV block at any anatomic level associated with any one of the following conditions:
  - Bradycardia with symptoms presumed to be due to AV block.
  - Arrhythmias and other medical conditions that require drugs that result in symptomatic bradycardia.
  - Documented periods of asystole  $\geq 3.0$  seconds or any escape rate  $<40$  beats per minute (bpm) in awake, symptom-free patients.
- Second-degree AV block regardless of type or site of block, with associated symptomatic bradycardia

- Infection of the implanted devices
- Persistent pain at the lead site not responsive to drug therapy.
- Allergic response to the implanted lead or materials used
- Lead, extension or migration that results in loss of ability to perform ScNS

The following adverse events will be managed medically

- Skin irritation related to prolonged placement of 7-day Mobile Cardiac Telemetry patch.
- Pain, goosebumps, hot flashes, and other uncomfortable feelings related to electrical stimulation of the subcutaneous nerves.

Alternative methods of treating drug resistant symptomatic AF include catheter ablation procedures and open-heart surgery, both carry significant risks of morbidity and mortality.

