#### 9.4.2 ANALYSIS OF THE PRIMARY EFFICACY ENDPOINT(S)

The primary endpoint is the average of AF burden at the end of the first week.

We will use Mobile Cardiac Telemetry to determine AF burden before surgery (eligibility visit), for two weeks during ScNS, 3 weeks following surgery and 3 months following surgery.

The average of AF burden at the end of the first week will be calculated per patient as the time spent in AF during the first week divided by the total time a patient is under observation during the first week. Change of the average AF burden from the baseline will be computed for each patient. The change in the average AF burden will be compared between group A (experimental) and group B (control) using the Wilcoxon rank sum test at a two-sided significance level of 0.025.

*The following secondary analyses of the primary endpoint will be performed:*

- 1) We will compare the baseline AF burden and the baseline number of Apple watch-detected AF episodes between groups. The number of Apple watch-detected AF will be standardized by the number of days that a subject is under observation in the respective time period. Further we will compare reduction in AF burden from baseline at weeks 1, 2, 3 and 12 in both Group A and Group B to test the null hypothesis that there is no reduction of AF burden in the two groups and between the two groups. We will also compare the reduction in the number of Apple watch-detected AF episodes from the baseline in the period between week-3 and the end of study in both Group A and Group B to test the null hypothesis that there is no difference in detected AF episodes in the two groups and between the two groups. Linear mixed effect models will be used for the comparisons, with Group, Week and Group by Week interaction as fixed effects, and a random intercept per subject. Week will be coded first as a categorical variable, and appropriate contrasts will be set up for the temporal comparisons. If outcome variables appear to be linear in time, we may model Week as a continuous fixed effect.
- 2) We may also compute the difference-in-difference statistics for the treatment for the 4 time intervals of the treatment, baseline and t weeks 1, 2, 3 and 12.

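### Section 7.2 lets unblinded investigators end follow-up for reasons that stimulation may itself produce, in conflict with 7.1; the later secondary comparisons are exposed, and the week-1 primary is largely spared

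*Combined protocol and SAP*

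**What the plan says.** Section 7.2 introduces its list of grounds with "An investigator may discontinue or withdraw a participant from the study for the following reasons". One ground is "If the participant meets an exclusion criterion (either newly developed or not previously recognized) that precludes further study participation"; another is that stimulation cannot be given once the electrode is in place, for whatever cause. Both lead to withdrawal from the study, not merely from stimulation.

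Section 7.1 says: "Discontinuation from electrical stimulation does not mean discontinuation from the study". It adds that the remaining procedures should be completed.

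Section 5.2 lists "Heart rate < 50 beats per minute in sinus rhythm on 12-lead ECG" as an exclusion, with no requirement for symptoms. Section 2.3.1 says of stimulation that "it is possible to slow down the sinus rate or atrioventricular (AV) conduction", and 7.2 itself says that "reduced sympathetic nerve discharges may be associated with reduced heart rate". Section 4.1 states: "The investigators are responsible for programming the device and cannot be blinded to the study". The Schedule of Activities (1.3) repeats the 12-lead ECG at weeks 1, 2 and 3 and at 3 months.

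Section 9.4.2 fixes the primary time point: "The primary endpoint is the average of AF burden at the end of the first week".

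**The concern.** Whether a randomised participant stays under observation should not depend on something the randomised treatment can change. Here it can. An exclusion criterion written for screening may be applied after randomisation, its trigger is one that active stimulation may cause and sham should not, and the person applying it knows the arm. The ground about undeliverable stimulation is also uneven between arms: it has obvious force for a device set at 3.5 mA and little for one set at 0 mA.

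If withdrawals fell more on Group A, the later between-group comparisons would no longer rest on the randomised groups. Section 7.2 does not replace participants withdrawn after receiving the intervention, and with 15 per arm a few losses matter. The conflict with 7.1 also means that two investigators facing the same patient could reasonably do opposite things.

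**Working it through.** **The plan's own figure.** No figure in the plan bears directly on this point, but the allowance for losses in 9.2 can be checked.
- Effect size: (76.3 − 5)/44.8 = 1.59.
- A t-test at two-sided 0.025 with 80% power needs 9 per arm. Dividing by 0.955 for the Wilcoxon test gives 9.42, so 10.
- With 70% retention, 10/0.70 = 14.3, so 15 per arm, as stated.

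This allowance covers the number lost. It does nothing about which participants are lost.

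**Which outcomes are exposed.** Assume withdrawal takes effect at a scheduled visit after that visit's assessments. AF burden is analysed at weeks 1, 2, 3 and 12 (9.4.2). Quality of life is collected after baseline at 3 weeks and 3 months (1.3, 9.4.3).

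| Visit whose ECG leads to withdrawal | AF burden lost | Quality of life lost |
|---|---|---|
| 1 week | weeks 2, 3, 12 (3 of 4) | 3 weeks, 3 months (2 of 2) |
| 2 weeks | weeks 3, 12 (2 of 4) | 3 weeks, 3 months (2 of 2) |
| 3 weeks | week 12 (1 of 4) | 3 months (1 of 2) |

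Ventricular rate comes from the same telemetry device (9.4.3), so its later values are lost with AF burden. The repeated recordings of skin sympathetic nerve activity are lost from the next visit on. Analyses fixed at the procedure day or week 1 are not affected.

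**Why the primary is largely spared.** The modified intention-to-treat set needs baseline and week-1 burden (9.3). The first scheduled clinic ECG after the implant day is at the 1-week visit, when the primary window is closing. A participant withdrawn there would normally already have the week-1 value. Exceptions are an earlier unscheduled ECG, a lost week-1 recording, or stimulation that fails in the first week and is followed by withdrawal. Such a participant leaves the primary set and is scored as zero reduction in the safety-set sensitivity analysis.

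**Whether the analysis repairs later losses.**
- Section 9.4.2 adjusts for baseline covariates if drop-out differs between groups. Baseline covariates do not capture a change in heart rate after randomisation.
- The mixed models contain group, week, their interaction and a random intercept. Sinus rate is not among them. The missing-at-random assumption stated in 9.4.3 fails if heart rate carries information about the missing outcome beyond those terms and the earlier outcomes.
- The sensitivity analysis carries the last value forward. For quality of life, a participant withdrawn at week 1 or 2 has only the baseline score to carry, so the change becomes zero by construction. For nerve activity, an on-stimulation value stands in for later visits.

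**Weight of each loss.** One withdrawal is 1/15 = 6.7% of an arm. At the planned retention, 0.70 × 15 = 10.5 remain, so one further loss is about 1 in 10.

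**The case against.** The strongest reply is that 7.2 is discretionary and limited to a criterion that rules out further participation. No passage says a sinus rate below 50 bpm does so. The bradycardia conditions that 2.3.1 and 7.2 list for termination concern AV block, which suggests that sinus slowing alone was not meant to end participation. ECGs are read by a core lab on a standard form (8.1), and the physicians responsible for ECG monitoring are blinded (4.1). The lead comes out at 2 weeks, so after that there is no stimulation to stop. The affected endpoints are secondary, mostly with nominal p values.

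Much of this stands. It rules out reading 7.2 as keeping the exclusion criteria in force as a binding rule. But no passage exempts sinus rate or says which criteria rule out participation, so the decision stays with staff who know the arm. Central reading standardises the trigger, not the decision. Removal of the lead does not remove the issue, because 2.3.2 suggests the autonomic effect may outlast stimulation.

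A reader might go further in three ways that the documents do not support.
- **Patients would be withdrawn for responding.** Slowing is described as possible, under risks. Response here means AF burden, and a link between the two is inference.
- **The systolic pressure exclusion works the same way.** No blood pressure measurement is in the Schedule of Activities, and no passage says stimulation lowers pressure.
- **The safety analysis would lose its bradycardia endpoint.** The bradycardia endpoints in 9.4.4 relate to AV block, the safety set is everyone who had lead surgery (9.3), and adverse events are recorded for 7 days, or 30 if serious, after participation ends (8.3.4). Observation would be shorter, but no listed endpoint disappears.

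**Conclusion.** The point holds as a conflict between 7.1 and 7.2 that opens a route to arm-dependent loss of follow-up. The route is permitted, not mandated. It threatens the week-2, week-3 and 3-month secondary comparisons and leaves the week-1 primary largely intact.

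The size cannot be stated. The documents give neither the sinus rates at entry nor the size or frequency of any fall, and crossing 50 bpm is not the same as being withdrawn. Any percentage would come wholly from assumed values. The direction is also conditional: if those lost were the Group A patients with the most AF benefit, the later comparisons would lean towards no effect, but the documents do not establish that they would be. The conclusion rests on two assumptions: that investigators would sometimes use the discretion, and that visit-based ECGs would be the usual trigger.

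**What to change.** Reconcile 7.2 with 7.1. For the exclusion-criterion ground and the ground about undeliverable stimulation, state three things:
- A condition that arises or is recognised after randomisation leads to a decision about stimulation under the existing safety passages.
- It does not by itself end follow-up. Unless consent is withdrawn or continued participation is against the participant's best interest, scheduled telemetry, ECG and questionnaires continue.
- The data are analysed in the randomised group.

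Both grounds need the change; amending only the first leaves the second as an open route to the same loss. Limiting the first to criteria known before randomisation would nearly empty it, since those participants are already screen failures under 5.4.

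The sponsor must also reconcile the safety passages themselves. For the same AV-block findings, 2.3.1 speaks of ending stimulation and 7.2 of ending the study. Which clinical rule applies is for the sponsor to settle.

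The reasons for withdrawal that 7.2 already records should be reported by group and visit.

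The cost is a short wording change and the follow-up of a few participants at visits already scheduled.
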